11 SOURCE DOCUMENTS AND ACCESS TO SOURCE DATA/DOCUMENTS

Study staff will maintain appropriate treatment and research records for this study, in compliance with ICH E6, Section 4.9 and regulatory and institutional requirements for the protection of confidentiality of subjects. Study staff will permit authorized representatives of NCI and regulatory agencies to examine (and when required by applicable law, to copy) research records for the purposes of quality assurance reviews, audits, and evaluation of the study safety, progress and data validity.

12 ETHICS/PROTECTION OF HUMAN SUBJECTS

12.1 Ethical Standard

The investigator will ensure that this study is conducted in full conformity with the principles set forth in The Belmont Report: Ethical Principles and Guidelines for the Protection of Human Subjects of Research, as drafted by the US National Commission for the Protection of Human Subjects of Biomedical and Behavioral Research (April 18, 1979) and codified in 45 CFR Part 46 and/or the ICH E6.

12.2 Institutional Review Board

The protocol, informed consent form(s), recruitment materials, and all subject materials will be submitted to the IRB for review and approval. IRB approval of the protocol and consent processes must be obtained before any subject is enrolled. Any amendment to approved study materials will require re-review and approval by the IRB before the changes are implemented in the study.

12.3 Informed Consent Process

Each person will provide consent to be screened for eligibility by phone. If screened eligible, they will provide verbal consent and be emailed a link to a study information sheet for their records. The study team may email a PDF as a back-up method if a participant is unable to open the study information sheet using the link.

Informed consent will include permission for contacting participants by push notification/mail/email/text to remind them of follow-up surveys and other study events and permission to collect all study data and track their use of the program. It will also include permission to order a 2-weekly supply of NRT patches from an online pharmacy and have it sent to participants' homes, for those participants meet the study requirements to receive the NRT and also specifically request for it to be mailed to them. (Note: receipt of the NRT is optional for participants.)

Participants are free to refuse to answer any survey questions or drop out of the study at any time. Participants will be instructed how to discontinue involvement in the intervention or drop out of the study as part of the consent process.

12.4 Exclusion of Women, Minorities, and Children (Special Populations)

Individuals of any gender or racial/ethnic group may participate. Children under the age of 18 years will be excluded.

12.5 Subject Confidentiality

Appropriate steps will be taken to safeguard participant confidentiality. This includes the following:

- KPWA is a HIPAA covered entity and complies with all HIPAA regulations regarding data security. All study files will be maintained in a centralized location on the KPWHRI

departmental server. Access to this data is password protected and subject to the same security protections as other confidential health plan data. Access will be limited to staff working on this study and require access to these files. All staff are trained in appropriate security protections, computer passwords are changed on a regular basis, and all staff sign annual confidentiality agreements.

- Participants' identities will not be shared with anyone other than relevant team members at KPWHRI as needed to perform their study roles.
- Electronic communications we send will not contain personal health information (PHI) other than references to smoking and participant first names.
- Biochemical confirmation of smoking abstinence will be remotely monitored using a secure video conference software for Apple and Android devices. The software does not store or access PHI, uses encrypted video streaming to protect confidentiality, and does not allow video sessions to be recorded, to further protect patient confidentiality.
- Participant information will not be stored on their phones. Data generated by the app will be encrypted when transmitted and then securely stored in a back-end database behind the KP firewall. Access will be limited to staff who need it, who will log-in using their NUID or other secure password (as recommended by KP).
- Data exported from the backend database will be stripped of identifiers before being stored or analyzed.
- Data from study surveys (collected in REDCap) will not be tied to personal identifiers.

12.6 Future Use of Identifiable Data

Identifiable information will be destroyed within 5 years of the end of the study, consistent with HIPAA and our IRB requirements.

We have no plans to retain identifiable information beyond this period. If this plan changes, we will obtain appropriate IRB approval and participant consent.

13 DATA HANDLING AND RECORD KEEPING

13.1 Data Management Responsibilities

Data collected will be captured in electronic records (e.g., REDcap).

Final datasets will be saved electronically, clearly labeled and stored in a secure project folder on the KPHRI server accessible only to study staff.

No electronic participant data shall be overwritten by study staff. As necessary, variables may be recoded into new variables for analyses, but will be done in a way to preserve the original record. All changes will be documented.

13.2 Types of Data

Data for this study will include eligibility screening, baseline and follow-up assessments, web analytics monitoring the program use, confirmation of smoking abstinence, and safety data.

13.3 Data Capture Methods

- Eligibility screening and consent will be completed by telephone and documented in REDCap.
- The baseline assessment will be completed by participants online in REDCap.
- Participants will be sent a link to complete the 1 and 3-month follow-up surveys online in REDCap. If unresponsive to the online survey, study staff may attempt to administer the assessment by phone.
- Video-based confirmation of smoking abstinence will be conducted using a secure telemedicine program. Participants will use saliva test kits mailed to them by the study. Results of biochemical confirmation of abstinence will be recorded in REDCap by study staff and a photo of the de-identified saliva test securely saved to the study files.
- Adverse events may be self-reported to study staff via email or by phone. Events will be documented in study records and followed up for resolution and stabilization, as appropriate. Adverse events will not be reported or tracked through the intervention/app.
- All electronic records will be kept in a 21 CFR Part-11 compliant data capture system, which includes password protection.

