3.3 Strategies for Recruitment and Retention

Recruitment:

Our primary strategy will be to recruit a nationwide sample of smokers using online postings, ads and message boards (e.g., Craigslist, Facebook, online newspapers).

If recruitment lags, we will seek IRB approval to expand enrollment to smokers enrolled in Kaiser Permanente Washington or recruit via community flyers.

Interested smokers will be directed to call the toll free study number at KPWHRI to learn more about the study and be screened for eligibility. We will adjust our recruitment posting, as needed, to ensure we meet our recruitment goal. Each participant will then be followed for ~3 months post-enrollment.

Retention:

Several steps will be taken to ensure participant retention, as follows:

- Participants will be compensated a \$25 e-gift card for completing the baseline and each follow-up survey, for \$75 total compensation.
- Participants will receive an additional \$20 e-gift card for providing timely biochemical confirmation of their smoking status via saliva testing following the 3-month survey.
- Assessments will be kept brief and will be available for completion online. If not completed online within 2 weeks, they will be offered by phone.
- We will collect multiple forms of contact information in order to track participants, including: mailing address, email address, and phone number(s).

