8 ASSESSMENT OF SAFETY

8.1 Specification of Safety Parameters

This is a minimal risk behavioral intervention. Nevertheless, adverse events (AEs) and serious adverse events (SAEs) will be recorded and reported over the course of the study.

An adverse event is any untoward or unfavorable medical occurrence in a human subject, including any abnormal sign (for example, abnormal physical exam or laboratory finding), symptom, or disease, temporally associated with the subject's participation in the research, whether or not considered related to the subject's participation in the research.

Project staff with participant contact will be trained to identify potential AEs and SAEs and instructed to report them immediately to the study PI and the project manager.

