8.2 Time Period and Frequency for Event Assessment and Follow-Up

Reportable events will be recorded in the data collection system throughout the study. Events will be followed for outcome information until resolution or stabilization.

The PI will record all reportable events with start dates occurring any time after informed consent is obtained until 7 (for non-serious AEs) or 30 days (for SAEs) after the last day of study participation.

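### The plan describes no adverse event question in the 1- and 3-month surveys, so the mild reactions it expects are likely to be under-ascertained, possibly more so among online completers

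*Combined protocol and SAP*

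**What the plan says.** Section 8.1 commits the study to safety recording: "adverse events (AEs) and serious adverse events (SAEs) will be recorded and reported over the course of the study". Section 8.2 adds "Reportable events will be recorded in the data collection system throughout the study", with a window running from consent "until 7 (for non-serious AEs) or 30 days (for SAEs) after the last day of study participation".

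The documents give two ways for an event to reach the record:

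- **Participant report.** Section 13.3: "Adverse events may be self-reported to study staff via email or by phone". The same bullet closes one channel: "Adverse events will not be reported or tracked through the intervention/app".
- **Staff recognition.** Section 8.1: "Project staff with participant contact will be trained to identify potential AEs and SAEs and instructed to report them immediately to the study PI".

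The 1- and 3-month surveys have their own bullet in section 13.3 and are not named there as an AE source. They are online first. Section 3.3 says of the assessments: "If not completed online within 2 weeks, they will be offered by phone".

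Section 8.1.4 lists what is expected: upset from the assessments, nicotine withdrawal in those who quit, and skin and general side effects in those who use the patches. Most of this is described as mild or transient.

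**The concern.** The commitment is to record events throughout the study, but both described routes are passive. One needs the participant to decide to write or call. The other needs the participant to be talking to staff for some other reason. Mild, self-limiting reactions of the kind listed in section 8.1.4 are easily left unmentioned unless someone asks.

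Several parts of the plan lean on good ascertainment. Section 8.3.2 treats frequency as part of what makes an event unexpected. Section 8.5 allows enrolment to be suspended on how often serious events occur. Section 7 makes the principal investigator the safety monitor, who can act only on what reaches the team. Section 2.1 makes planning a future efficacy trial an objective, and section 10.1 predicts more patch use in the experimental arm. The pilot's AE counts, overall and by arm, would be natural input to that planning.

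**Working it through.** The plan gives no AE rate, capture rate, phone share or safety precision target, and the sample size of 60 (section 10.2) rests on a guideline for pilot studies. There is no figure to reproduce, so the main check is a reading of the sections against each other.

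**Contact path of a participant who does everything online**

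1. Screening and verbal consent: by phone with staff (sections 5.1, 12.3).
2. Baseline survey and randomisation: online and automatic (section 5.2).
3. App set-up: emailed instructions, with staff help only if needed (sections 4.2, 5.2).
4. Patches, if earned and requested: mailed from an online pharmacy (section 12.3).
5. Surveys at 1 and 3 months: online; phone is for those who have not completed within 2 weeks (sections 3.3, 13.3).
6. Video saliva check: section 5.4 dropped it from the final plan and says that not all non-smokers had been flagged for it. It cannot be counted on as contact with people who stopped smoking.
7. The 7 or 30 days after participation ends (section 8.2): no contact is described.

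After step 1, this participant has no scheduled conversation with staff. A phone completer has at least one. The outcomes in section 2.2 include no safety measure, and section 10.3 includes no AE summary.

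**Illustration of size (every rate below is an assumption)**

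Let N = 60, p = true share with an event, f = phone share, and c = capture probability by mode.

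Recorded cases = N × p × [(1 − f) × c_online + f × c_phone].

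- Low end: p = 0.20, f = 0.1, c = 0.1 online and 0.5 phone. Overall capture = 0.9 × 0.1 + 0.1 × 0.5 = 0.14. Of 12 true cases, 12 × 0.14 = 1.7 are recorded.
- High end: p = 0.20, f = 0.5, c = 0.5 online and 0.9 phone. Overall capture = 0.5 × 0.5 + 0.5 × 0.9 = 0.70. Of 12 true cases, 8.4 are recorded.

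Chance of recording at least one case of a 5% event among 60: 1 − 0.95^60 = 95% with full capture. With 30% capture the recordable rate is 0.05 × 0.3 = 0.015, and 1 − 0.985^60 = 60%.

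Upper limit after zero recorded events (one-sided 95%): 1 − 0.05^(1/60) = 4.9% with full capture. Dividing by assumed capture gives 4.87/0.5 = 9.7% or 4.87/0.25 = 19.5%. These limits apply only to events that all 60 could have. Patch reactions can occur only in patch users, and quit-related withdrawal only in those who try to quit. Those numbers at risk are unknown and may be well below 60.

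**Comparison by arm (true relative risk of 1)**

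- Equal phone share in both arms, for example 30% and 30%: apparent relative risk 1.00.
- Phone share 40% experimental and 20% control, c = 0.1 and 0.5: (0.6 × 0.1 + 0.4 × 0.5)/(0.8 × 0.1 + 0.2 × 0.5) = 0.26/0.18 = 1.44. With c = 0.5 and 0.9: 0.66/0.58 = 1.14.
- Phone shares reversed: 0.69 and 0.88.

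A distortion by arm therefore needs a difference between arms in phone share or in capture. The documents give no figure for either.

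**The case against.** A reader might infer that events are captured only when participants write or call. The text does not say this. Section 13.3 is permissive, and section 8.1 provides that "Project staff with participant contact will be trained to identify potential AEs and SAEs", a route that also works in calls that staff start. Any unevenness by survey mode in fact depends on that second route. This objection stands.

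A reader might also infer that events certainly will be under-counted. The survey instruments are not shown, and section 6 leaves procedural detail to a Manual of Procedures that is not among the documents. An AE item may exist. Excluding the app does not settle the matter, because the surveys run in REDCap. Nor does section 13.2, which merely lists safety data among the types of data. Only a likely shortfall, on the methods as described, is supported.

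On consequences, safety is neither an objective nor a listed outcome, section 10.3 plans no AE comparison by arm, and no section says that a low count will be taken as evidence of safety. The study is classed as minimal risk, the patches are optional, over the counter and available in both arms, and section 7 scales monitoring to risk. This limits the severity. It does not remove the mismatch between a commitment to record events throughout and methods that describe no enquiry.

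Finally, section 5.4 describes a programming error at the 3-month assessment in the past tense, so follow-up may have been under way or finished when this version was written. New items added part-way would themselves make ascertainment uneven. This stands, and the fix has to allow for it.

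**Conclusion.** The point holds in a limited form. As described, AE capture rests on spontaneous report and on recognition by staff who happen to be in contact, with no AE question described at either survey. The mild reactions in section 8.1.4 are likely to be under-ascertained, possibly more among online completers. This assumes that the unseen surveys and manual contain no such question, and that people volunteer mild events less often than they report them when asked.

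The size cannot be fixed from the documents. The assumed capture rates above span 14% to 70% overall and serve only as illustration. Bias between arms is conditional, and the documents do not support asserting it. In a minimal-risk pilot this is something that should be corrected, but it does not undermine the trial.

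**What to change.** State in section 13.3 whether the 1- and 3-month surveys ask about AEs. If they do not and follow-up has yet to take place:

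- Add the same few items to the online and phone versions in both arms: any new or worse health problem, any hospital or emergency visit, any patch use with a reaction, any distress from the study.
- Place them before the final survey section, which reveals the arm to telephone staff (section 3.4.2).
- Have a positive answer alert the project manager and prompt staff follow-up.
- List the surveys as an AE source. Keep email and phone for events between surveys and in the window after participation ends, which the surveys do not reach.
- Add to section 10.3 a descriptive summary by arm, with elicited and spontaneous events shown separately.

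The cost is about four survey items, a REDCap alert, an IRB amendment and a few call-backs among about 60 people. More mild events will be recorded.

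If follow-up is under way, record the date of the change and separate events by whether the participant was asked. If follow-up is complete, report the counts by arm as spontaneously reported or staff-identified, do not read low counts as evidence of safety, and build the items into the future trial.

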13.4 Study Records Retention

All study data will be maintained for at least 5 years after the conclusion of the study. At that time, consistent with HIPAA guidelines, identifying information and linking files will be destroyed unless consent to retain these files is granted by study participants or the IRB.

13.5 Protocol Deviations and Violations

All staff will immediately report protocol deviations and violations to the KPHRI Project Manager, who will inform the PI. Deviations will be considered any noncompliance with this clinical trial protocol, Good Clinical Practice, or the Manual of Procedures.

Protocol deviations will be reported annually to the IRB. Protocol violations will be reported to the IRB in a timely manner.

